## STUDY SUMMARY

Study title:	An Observational Study "FOLLITROPIN" Comparing the Efficacy of Follitropin Alpha Biosimilar: The Real-world Data
Study type:	Phase IV
Test product	
TN: Primapur®
 
INN: follitropin alpha
 
Dosage form: solution for subcutaneous injection
 
Pharmaceutical form: pre-filled disposable syringe containing follitropin alpha 66 µg (900 IU), 33 µg (450 IU), 22 µg (300 IU),
 
Manufacturer: Zavod Medsintez LLC, Russia

Ethical and legal aspects:	
This study conducted in strict accordance with the following international and Russian documents:
 
 
1. Principles of the World Medical Association Declaration of Helsinki (Fortaleza, Brazil, 2013).
 
2. Constitution of the Russian Federation.
 
3. Federal Law "On the fundamentals of protecting the health of citizens in the Russian Federation" dated November 21, 2011 No. 323-FZ, 2011.
 
4. Federal Law "On the Circulation of Medicines" No. 61-FZ dated 12 April 2010.
 
5. Federal Law "On personal data" No. 152-FZ dated July 27, 2006.
 
6. Order of the Ministry of Health of the Russian Federation "On the use of assisted reproductive technologies, contraindications and limitations to their use" No. 107 n dated August 30, 2012.
 

Study goals:	To investigate the efficacy of follitropin alpha biosimilar therapy (Primapur ® ) in nonselected real-world population.
Study objectives:	
The efficacy and safety of biosimilar follitropin alpha have been demonstrated in randomized blinded prospective clinical trials of phases I and III. Unfortunately, there is a gap between the clinical trials and real clinical practice data. The real-world patient data helps to create an evidence-based background for successful implementation of medicine at everyday practice in a nonselected population. The ovarian stimulation (OS) protocols included: monotherapy protocols with using only follitropin alpha biosimilar (Primapur®); mixed protocols (recombinant and urinary-derived gonadotropins) and follitropin alpha biosimilar; short protocols with using antagonists of gonadotropin-releasing hormone (GnRH) and long protocols with

	GnRH agonists. The stimulation protocols were analyzed with Primapur® application for at least 5 days.
Study design:	Retrospective, observational (non-interventional), anonymized, cohort study
Number of patients	5500 patients
Study centers	35 in vitro fertilization (IVF) clinics in the Russian Federation
Study population:	Women aged 20-43 with established causes of infertility and indications for the use of assisted reproductive technologies (ART) and ovarian stimulation.
Inclusion criteria:	
 
1. Women with established causes of infertility and indications for the use of ART methods, according to the Order of the Ministry of Health of the Russian Federation "On the use of assisted reproductive technologies, contraindications and limitations to their use" No. 107 n dated August 30, 2012.
 
2. Infertility due to female and/or male factor.
 
3. Presence of ovaries accessible for aspiration of follicles.
 
4. Anatomical and functional capability of uterus to bear pregnancy.
 

Exclusion criteria:	
 
1. Women with established contraindications to the use of ART methods, according to the Order of the Ministry of Health of the Russian Federation "On the use of assisted reproductive technologies, contraindications and limitations to their use" No. 107 n dated August 30, 2012.
 
2. Presence of pregnancy
 
3. Hypersensitivity to follitropin alpha and other gonadotropins or excipients.
 
4. Ovarian cysts (not associated with polycystic ovarian syndrome), uterine hemorrhage of unclear etiology
 
5. Premature ovarian failure
 
6. Presence of clinically significant systemic disease
 
7. Presence of chronic cardiovascular, hepatic, renal or pulmonary disease
 
8. Neoplasia
 
9. Narcomania, alcoholism
 

Dosage and duration of treatment; route of administration:	
Drug: Follicle Stimulating Hormone/Luteinizing Hormone
 
Overall ovarian stimulation protocols with follitropin alpha biosimilar for at least 5 days (100-300 IU) and other recombinant follitropins and menotropins, short (antagonists of GnRH) or long protocols (agonist of GnRH).

Concomitant therapy:	All patients received approved medication by physician, accordingly to National guidelines.


Efficacy evaluation criteria:
	
Study endpoints per patient:
 
Primary point:
 
 
• Total number of aspirated oocytes.
 
• Incidence of clinical pregnancies (up to 6 weeks after the embryo(s) transfer).
 
 
Secondary points:
 
 
• Number of mature oocytes (MII stage).
 
• Number of fertilized oocytes (zygotes with 2PN).
 
• Total dose of a follitropin alpha biosimilar injected (IU).
 

Safety evaluation criteria:
	
 
• Incidence of serious adverse events e.g., severe ovarian hyperstimulation syndrome (%) with hospitalization.
 
• Incidence of the adverse event, such as injection site pain (%).
 

Groups/arms to compare:
	
 
1. Monoprotocols: follitropin alpha biosimilar only and antagonists/agonists of GnRH (The ovarian stimulation (OS) protocols included monotherapy protocols with using follitropin alpha biosimilar only and antagonists/agonists of gonadotropin-releasing hormone (GnRH): ganirelix, cetrorelix, triptorelin, buserelin).
 
2. Mixed protocols: recombinant and urinary-derived gonadotropins and antagonists/agonists of GnRH. (The OS protocols included: mixed protocols (recombinant with addition of urinary-derived gonadotropins) and antagonists/agonists of GnRH (ganirelix, cetrorelix, triptorelin, buserelin), where follitropin alpha biosimilar used for at least 5 days during OS).
 
3. Monoprotocols: follitropin alpha biosimilar only and antagonists of GnRH (The OS protocols included: monotherapy protocols with using only follitropin alpha biosimilar and antagonists of GnRH).
 
4. Monoprotocols: follitropin alpha biosimilar only and agonist of GnRH (The OS protocol included: monotherapy protocols with using only follitropin alpha biosimilar and agonists of GnRH).
 
5. The overall protocols (The OS protocols included: (1) Monoprotocols: follitropin alpha biosimilar only and antagonists/agonists of GnRH, (2) Mixed protocols: recombinant and urinary-derived gonadotropins and antagonists/agonists of GnRH).
 

	
Flow chart:
 <pre> graph TD     A[Overall protocols] --> B[Monoprotocols]     A --> C[Mixed protocols]     B --> D[Monoprotocols with antagonist GnRH]     B --> E[Monoprotocols with agonist GnRH] </pre>

Outcome Measures:
	
Primary outcomes:
 
 
1. Number of Oocytes Retrieved
 
2. Percentage of Participants With Ongoing Clinical Pregnancy Per Embryo Transfer
 
 
Secondary outcomes:
 
 
1. Number of Mature Oocytes
 
2. Number of Fertilized Oocytes
 
3. Total Dose of Follitropin Alpha Biosimilar Protocol
 

Groups/Arms to compare
	
 
1. Mixed protocols: recombinant and urinary-derived gonadotropins and antagonists/agonists of GnRH AND Monoprotocols: follitropin alpha biosimilar only and antagonists/agonists of GnRH
 
2. Monoprotocols: follitropin alpha biosimilar only and antagonists of GnRH AND Monoprotocols: follitropin alpha biosimilar only and agonist of GnRH
 
3. Overall protocols – descriptive statistics for all in vitro fertilization protocols
 

Statistical processing of data:
	
Description of methods of statistical data processing
 
The quantitative data obtained during the study will be tested for normal distribution, using the Shapiro-Wilk test and, if necessary, the F-test of equality of variances. For variables corresponding to the normal distribution, mean values and standard deviation of the mean will be calculated; Quantitative data not corresponding to the normal distribution will be described using the median and interquartile interval. Qualitative variables will be described using absolute and relative frequencies (percentages).

In order to compare two groups of normally distributed quantitative data, the Student's t-test will be used; if quantitative data distribution differs from normal values, the Mann-Whitney U test will be used. For intergroup comparisons by qualitative characteristics, the Fisher's exact test will be used.

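### Every group contains the biosimilar, so neither planned test isolates its efficacy, and the outcomes that do answer the goal get no confidence interval

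*Combined protocol and SAP*

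**What the plan says.** All references are to the Study Summary of the combined protocol and SAP.

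- **Purpose.** The title reads "Comparing the Efficacy of Follitropin Alpha Biosimilar", followed by a reference to real-world data. The Study goals row says "To investigate the efficacy of follitropin alpha biosimilar therapy" in an unselected population. The Study objectives row gives the motive: efficacy has already been shown in phase I and III trials, but "there is a gap between the clinical trials and real clinical practice data".
- **Exposure.** The Study objectives row ends: "The stimulation protocols were analyzed with Primapur® application for at least 5 days".
- **Groups.** The first Groups/arms to compare row defines five. Groups 1, 3 and 4 are mono protocols, with the biosimilar as the only gonadotropin. Group 2 is the mixed protocols, "where follitropin alpha biosimilar used for at least 5 days during OS". Group 5 pools groups 1 and 2.
- **Comparisons.** The second Groups/Arms to compare row plans mixed against mono, and mono with antagonist against mono with agonist. The overall group receives "descriptive statistics for all in vitro fertilization protocols".
- **Methods.** The Statistical processing row gives mean and SD, or median and interquartile interval, depending on a normality test. Qualitative variables get counts and percentages. Groups are compared by t-test or Mann-Whitney test, and by Fisher's exact test, at two-sided 0.05. No confidence interval, benchmark, margin or covariate adjustment is mentioned.
- **Design and size.** "Retrospective, observational (non-interventional), anonymized, cohort study", with "5500 patients" from 35 clinics and no derivation of that number.

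**The concern.** To say how well a drug works relative to something else, a contrast needs a side without the drug, or an external standard. The plan has neither. Its only inferential machinery, the tests at 0.05, is attached to two contrasts that ask other questions: whether other gonadotropins are added, and which GnRH analogue is used.

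Interpretation is what is at stake. Under this title, a non-significant mono-versus-mixed result could be taken as equivalence of the biosimilar, and a significant one as superiority or inferiority. Neither would follow. Meanwhile the results that bear on the gap between trials and practice, namely outcomes in women stimulated with the biosimilar, come with no statement of their precision.

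**Working it through.** **1. What each group and contrast contains**

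| Group | Biosimilar present? |
|---|---|
| 1 Mono, antagonist or agonist | Yes, only gonadotropin |
| 2 Mixed | Yes, at least 5 days |
| 3 Mono, antagonist | Yes, only gonadotropin |
| 4 Mono, agonist | Yes, only gonadotropin |
| 5 Overall (1 + 2) | Yes |

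Biosimilar-free groups: 0 of 5. Planned contrasts with a biosimilar-free side: 0 of 2.

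**2. What the mixed-versus-mono test responds to**

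This illustration uses assumed values: a base mean of 2 oocytes, biosimilar effect b, added-gonadotropin effect u, SD 6, and 5500 women split 70:30 (3850 mono, 1650 mixed).

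- Mono mean = 2 + b. Mixed mean = 2 + b + u. Mono minus mixed = −u, so b cancels.
- Standard error = 6 × √(1/3850 + 1/1650) = 0.177. For u = 0.5, power ≈ Φ(0.5/0.177 − 1.96) ≈ 0.81. This is the same for b = 0, 4 or 8.

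Under the same additive reasoning, b also cancels from antagonist versus agonist.

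**3. Where some information could leak in**

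The dosage row allows other recombinant follitropins and menotropins, and the mixed group needs only 5 biosimilar days. Suppose a share s of the biosimilar's effect is replaced by another gonadotropin with an assumed effect of 8.

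- Mixed mean = 2 + (1 − s)b + 8s. Mono minus mixed = s(b − 8).
- With s = 0.25, the contrast is −2, −1 and 0 for b = 0, 4 and 8.

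In this case the first contrast does move with b. The information is relative to whatever replaced the biosimilar, scaled by an unknown share, and confounded by the reasons for choosing a mixed protocol. The planned tests make no adjustment for those reasons.

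**4. The stated sample size**

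The figure of 5500 cannot be reproduced, because the plan gives no effect size, SD, event rate, margin or power.

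**5. What estimation could deliver in the overall cohort**

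The SD, ICC, pregnancy rate and number of transfers are assumptions. The 5500 and 35 come from the plan.

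- Oocytes, no clustering: 1.96 × 6/√5500 = 0.159. With SD 5 to 7 the range is 0.132 to 0.185.
- Clinic size, if equal: 5500/35 ≈ 157. With ICC 0.02 the design effect is 1 + 156 × 0.02 ≈ 4.1 and its square root is about 2.03. The half-width becomes 0.159 × 2.03 ≈ 0.32. With SD 5 to 7 the range is about 0.27 to 0.38.
- Pregnancy at 35%, before clustering. The Outcome Measures row counts pregnancy per embryo transfer, so the denominator may be below 5500.
  - 5500 transfers: 1.96 × √(0.35 × 0.65/5500) = 1.26 percentage points.
  - 3000 transfers: 1.96 × √(0.35 × 0.65/3000) = 1.71 percentage points.
  - Clustering would widen both.

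The mono cohort is smaller than 5500 by an amount the plan does not state, so its intervals would generally be wider.

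**The case against.** The strongest reply is that the plan never promises a comparison with the originator or any other follitropin. It lists exactly which groups are compared, and the word comparing in the title can be read as comparing efficacy across protocols. The goal is to investigate, efficacy is said to be established already, and a descriptive cohort with regimen comparisons is a legitimate design for that purpose. The plan also makes no equivalence claim, so the misreading is a risk in reporting and not something it states.

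Most of this stands, and it limits the point. Four stronger readings are tempting, and the documents do not support them.

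- **The tests carry no information at all on the biosimilar.** Its share of stimulation may differ between mono and mixed protocols, so the first test may carry some, though indirect and confounded.
- **Only the overall group bears on the goal.** The mono groups do too, and arguably more cleanly.
- **The descriptive statistics are unspecified.** They are specified, and the same rules apply to every group. What is missing is a confidence interval.
- **The phase III results are the plan's benchmark.** They are mentioned without figures and are not named as a reference.

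What the reply does not remove is the mismatch. If the study is descriptive, estimates with stated precision should lead, and the title should not suggest a comparison of the biosimilar's efficacy.

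**Conclusion.** The point holds as a mismatch between stated purpose and planned inference. None of the five groups is free of the biosimilar and neither test has a biosimilar-free side, so neither test isolates its efficacy. A larger sample would not change that. This conclusion rests on the group definitions alone and needs no numerical assumption.

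A reader might go further and infer that the study cannot meet its goal. That does not follow: the mono and overall cohorts can describe real-world outcomes, possibly with useful precision. The half-widths above are illustrations, not predictions. They depend on the assumed SD, pregnancy rate, number of transfers and ICC, and on equal clinic sizes. The flaw can be corrected and does not undermine the data collection.

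**What to change.** 1. Make estimation the primary analysis: mean oocytes retrieved and clinical pregnancy rate per embryo transfer, each with a 95% confidence interval that allows for clustering by clinic, in the mono and overall cohorts. Report the mean and its interval whatever the normality test shows, and state the number of transfers.
2. Label mixed versus mono, and antagonist versus agonist, as exploratory comparisons of stimulation regimen. State that their p-values are not evidence of the biosimilar's efficacy or equivalence.
3. Reword the title and goal to describe real-world outcomes of ovarian stimulation with the biosimilar.

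This needs no new arm, patients or data. It costs some redrafting and a little more analysis for the clustered intervals. The sponsor also gives up a comparative-efficacy claim that the design cannot support.

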**Applicable significance level**

In this study, the indicators are considered statistically significant at the bilateral p-value level  $<0.05$ .

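### Both planned comparisons pool 35 clinics with unadjusted tests, so they are confounded if protocol use and outcomes both differ by clinic

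*Combined protocol and SAP*

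**What the plan says.** The Study Summary gives the design as "Retrospective, observational (non-interventional), anonymized, cohort study", with "5500 patients" from "35 in vitro fertilization (IVF) clinics in the Russian Federation". Treatment followed routine practice: "All patients received approved medication by physician, accordingly to National guidelines".

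The second of the two entries on groups to compare sets up two inferential contrasts. The first sets "Mixed protocols: recombinant and urinary-derived gonadotropins and antagonists/agonists of GnRH" against monoprotocols. The second sets antagonist against agonist within the monoprotocols. The overall group is descriptive only.

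The section on statistical processing names Student's t-test for normally distributed data. Otherwise, "if quantitative data distribution differs from normal values, the Mann-Whitney U test will be used". For categorical outcomes, "For intergroup comparisons by qualitative characteristics, the Fisher's exact test will be used". Under the significance-level heading, "the indicators are considered statistically significant at the bilateral p-value level" below 0.05.

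Clinic appears only as a count of centres. There is no stratification, regression, matching, clinic effect, clustered variance or by-clinic table, and the documents do not describe how protocol use is spread over the clinics.

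**The concern.** All three tests treat the patients as independent and exchangeable between groups. Here the protocol was chosen in practice, so group membership may partly reflect which clinic a woman attended. Oocyte yield and pregnancy may also differ by clinic, for example through patient mix or laboratory practice. When both vary, the two groups contain different mixtures of clinics, and a pooled test attributes the resulting difference to the protocol.

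Two effects should be kept apart:

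- If clinic outcome level and protocol preference vary independently, the estimate is unbiased over repetitions. Any one study still carries a chance clinic imbalance that the test ignores, so p-values are too small.
- If the two are correlated across clinics, the estimate is also systematically biased.

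At stake are the p-values for both primary outcomes, oocytes retrieved and clinical pregnancy. The large sample gives no protection, because it makes small clinic-driven differences statistically significant.

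**Working it through.** **Inputs.** From the Study Summary: 5500 patients, 35 clinics, two-sided 5%. The documents give no power, effect size, SD, event rate or group split, so the 5500 cannot be reproduced. Everything else below is assumed: outcome intra-clinic correlation (ICC) 0.01 to 0.05, intra-clinic correlation of protocol choice (ρ) 0, 1/11 ≈ 0.09 or 0.25, and equal clinic sizes, m = 5500/35 = 157.1.

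**Formula.** With clinic outcome level and protocol choice independent, the variance of the pooled difference is inflated by

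DE = 1 + (m − 1) × ICC × ρ,

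and the actual type I error is 2 × [1 − Φ(1.96/√DE)].

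Example: ICC 0.02, ρ 0.25 gives DE = 1 + 156.1 × 0.02 × 0.25 = 1.78; 1.96/√1.78 = 1.47; error 14.2%.

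**Comparison 1 (mixed versus mono)**

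| ICC | DE, ρ = 0.09 | Error | DE, ρ = 0.25 | Error |
|---|---|---|---|---|
| 0.01 | 1.14 | 6.7% | 1.39 | 9.6% |
| 0.02 | 1.28 | 8.4% | 1.78 | 14.2% |
| 0.05 | 1.71 | 13.4% | 2.95 | 25.4% |

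With ρ = 0, DE = 1 and the error is 5%.

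**Comparison 2 (antagonist versus agonist).** If 50% to 70% of patients had a monoprotocol (assumed), m is 79 to 110. At ICC 0.02, DE is 1.14 to 1.20 for ρ = 0.09 (error 6.7% to 7.3%) and 1.39 to 1.55 for ρ = 0.25 (9.6% to 11.5%).

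**Simulation with no correlation between outcome level and protocol preference.** 35 clinics of 157, no true protocol effect, assumed pregnancy rate 35%, assumed mean mixed share 10%, 30% or 50%, 2000 runs (Monte Carlo SE 0.5 to 1.0 points):

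| ICC | ρ | Mann-Whitney | Fisher |
|---|---|---|---|
| 0.02 | 0 (share 30%) | 5.4% | 4.4% |
| 0.02 | 0.09 | 7.8–8.8% | 7.4–8.2% |
| 0.02 | 0.25 | 12.8–14.6% | 12.2–13.8% |
| 0.05 | 0.25 | 22.8–24.6% | 23.8–25.0% |

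On the same data, across all 13 scenarios run, clinic-stratified tests stayed at 4.0% to 6.4% (van Elteren) and 4.4% to 5.7% (Cochran-Mantel-Haenszel).

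**Simulation with correlation.** A separate simulation used a mean split of about 50:50, a between-clinic SD of 1 in the log-odds of protocol use, and ICC 0.05 (on the log-odds scale for pregnancy):

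| Correlation across clinics | Mann-Whitney | Fisher | Mean bias |
|---|---|---|---|
| 0 | 19.9% | 15.7% | about 0 |
| 0.3 | 50.8% | 45.8% | 0.057 SD; 2.3 percentage points |
| 0.5 | 81.3% | 72.3% | 0.092 SD; 3.7 percentage points |

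For scale, 5500 patients split 50:50 have 80% power for a difference of 0.076 SD. Over all scenarios in this simulation, clinic-adjusted analyses stayed at 3.7% to 6.2% (quantitative) and 4.2% to 5.8% (pregnancy), with bias of at most about 0.001 SD or 0.1 percentage points.

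**The case against.** The strongest reply is that the harm is conditional and its size assumed. The documents supply only 5500 and 35, and the illustrated error for the uncorrelated case runs from 5%, which is no problem, to about 25%. That stands: the missing clinic term is certain, the damage is not. But the plan has no step that would reveal which case applies.

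Four narrower points:

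- **Inflation is not bias.** The design-effect formula measures false positives from ignored clustering. Systematic bias needs clinic outcome level and protocol preference to be correlated. This is correct. With 35 clinics that differ on both, however, a single study will still be imbalanced, and its p-values will be too small.
- **Pregnancy denominator.** One of the two outcome lists defines pregnancy per embryo transfer, so 157 per clinic is too many for that version. If 60% to 80% had a transfer (assumed), m is 94 to 126, and at ICC 0.02 the error is 7.0% to 7.7% (ρ = 0.09) or 10.6% to 12.4% (ρ = 0.25). This trims the figure without removing it. Unequal clinic sizes work the other way: with an assumed coefficient of variation of 0.8, replacing m by m(1 + 0.8²) = 257.7 gives 10.6% and 19.5% in place of 8.4% and 14.2%.
- **Limited cure.** The simulated good behaviour of the stratified tests assumes no patient-level selection within clinics. Women may be given a mixed protocol because of age or expected response, and clinic adjustment leaves that untouched. This stands and needs separate covariate adjustment.
- **Biosimilar dose.** Mixed protocols add other gonadotropins by definition, so a difference in biosimilar dose in comparison 1 is partly built in. A no-effect error rate means little for that outcome.

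Finally, no confirmatory hypothesis is stated, which lowers the stakes. Even so, two group comparisons are to be called significant or not at 5%.

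**Conclusion.** The concern holds. Both comparisons rest on pooled, unadjusted tests in a non-randomised 35-clinic cohort. If protocol use and outcomes both vary by clinic, the plan cannot separate a clinic effect from a protocol effect, and its type I error exceeds the stated 5%.

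At an outcome ICC of 0.02 the error is about 8% to 14% for comparison 1 and 7% to 11.5% for comparison 2. It is higher if the ICC or the spread in clinic sizes is larger, and far higher if clinic outcome level and protocol preference are correlated. It is about 5% if the protocol mix is the same everywhere or outcomes do not differ by clinic. Confidence is high that the adjustment is absent and that the mechanism is real; the size depends entirely on the assumed correlations. The plan should be changed, because the change is cheap and the clinic pattern can be checked in the data, provided a clinic code is held.

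**What to change.** 1. Add a table of protocol mix and of each primary and secondary outcome by clinic.
2. Make both comparisons within clinic: van Elteren for oocyte counts and dose and Cochran-Mantel-Haenszel for pregnancy, or regression models with a clinic effect.
3. Report each estimate with a 95% confidence interval. Van Elteren gives only a test, so the estimate for quantitative outcomes should come from the regression model; for pregnancy, the Mantel-Haenszel estimate or a regression model will serve.
4. Keep the planned unadjusted tests as a sensitivity analysis.
5. Deal with patient-level confounding by indication separately, through covariate adjustment.

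**Cost.** SAP wording and one table. The data are described as anonymized, so the sponsor must first confirm that a clinic code is retained; without one this cannot be done. Intervals widen by a factor of √[(1 − ICC)/(1 − ρ)] relative to the unadjusted ones. At ICC 0.02 this is √(0.98/0.909) = 1.04 for ρ = 0.09 and √(0.98/0.75) = 1.14 for ρ = 0.25, that is, about 4% to 14% wider. Clinics that used only one protocol contribute little or nothing to the within-clinic comparison, and the by-clinic table will show how many there are.

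### Both planned group comparisons set non-randomised groups against each other with unadjusted tests only, so a significant difference in oocytes or pregnancy cannot be attributed to the regimen.

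*Combined protocol and SAP*

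**What the plan says.** The Study Summary of the combined protocol and SAP describes the design as "Retrospective, observational (non-interventional), anonymized, cohort study". The population is "Women aged 20-43 with established causes of infertility", drawn from "35 in vitro fertilization (IVF) clinics in the Russian Federation", with 5500 patients in total.

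The groups are defined by the drugs used in the cycle. Monoprotocols are "monotherapy protocols with using follitropin alpha biosimilar only" plus a GnRH antagonist or agonist. Mixed protocols are described as "mixed protocols (recombinant with addition of urinary-derived gonadotropins", also with an antagonist or agonist. The second Groups/Arms to compare row sets up two contrasts: mixed versus mono, and antagonist mono versus agonist mono. The overall group is descriptive only.

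The primary outcomes are oocytes retrieved and clinical pregnancy. Under Statistical processing of data the comparative methods are these:

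- for continuous data, "In order to compare two groups of normally distributed quantitative data, the Student's t-test will be used", with the Mann-Whitney U test if normality fails;
- for categorical data, "For intergroup comparisons by qualitative characteristics, the Fisher's exact test will be used".

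The significance level is two-sided 0.05. No regression, propensity score, matching, stratification, covariate list, clinic term or sensitivity analysis for confounding appears anywhere. Nor is there any account of how or when a woman came to be in one group rather than another. The concomitant therapy row mentions the physician and national guidelines, but it gives no rule for the choice of regimen.

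**The concern.** The title announces a study "Comparing the Efficacy of Follitropin Alpha Biosimilar", and two contrasts on primary outcomes carry a significance threshold. A p-value below 0.05 will invite the reading that one regimen performs better than the other.

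Without randomisation, women on different regimens may differ in age, in other prognostic factors or in the clinic that treated them. Any of these can shift oocyte yield or pregnancy. An unadjusted two-sample test answers only whether the groups differ, not why. With 5500 patients it is sensitive enough that a small imbalance can produce significance by itself. This applies to comparison 2 as well as comparison 1, and to pregnancy as well as oocytes.

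**Working it through.** **No figure to reproduce.** The plan gives 5500 patients without power, effect size, SD, pregnancy rate or group split. The check therefore asks how often the stated tests would reject if the regimens had no effect and the groups merely differed at baseline.

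**Inputs from the documents:** N = 5500; two-sided alpha 0.05 (critical value 1.96).

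**Assumed inputs:** SD 6 oocytes; a baseline factor differing by d = 0.25 SD between groups and correlated rho = 0.3 with yield; splits of 50:50, 80:20 and 90:10; no true effect.

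**Formulas**
- Spurious gap = SD × d × rho = 6 × 0.25 × 0.3 = 0.45 oocytes.
- SE = 6 × sqrt(1/n1 + 1/n2).
- Rejection rate = Phi(gap/SE − 1.96) + Phi(−gap/SE − 1.96).

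| Split | n1, n2 | SE | gap/SE | False rejection |
|---|---|---|---|---|
| 50:50 | 2750, 2750 | 0.162 | 2.78 | 79% |
| 80:20 | 4400, 1100 | 0.202 | 2.22 | 60% |
| 90:10 | 4950, 550 | 0.270 | 1.67 | 39% |

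Gap and SE both scale with the SD, so these rates do not depend on the assumed 6.

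**Range over d and rho.** For d from 0.1 to 0.3 and rho from 0.2 to 0.4, the gap runs from 6 × 0.1 × 0.2 = 0.12 to 6 × 0.3 × 0.4 = 0.72 oocytes. The rejection rate runs from 11.5% to 99% at 50:50, 9% to 95% at 80:20, and 7% to 76% at 90:10.

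**Pregnancy.** Assumed: 35% rate, correlation of 0.2 to 0.3 between the factor and the underlying liability, d = 0.25, 50:50 split, every patient with a transfer.
- Gap = 0.25 × r × phi(z at 0.35), with phi = 0.370. This gives 1.9 points at r = 0.2 and 2.8 points at r = 0.3.
- SE = sqrt(2 × 0.35 × 0.65 / 2750) = 1.29 points.
- Rejection: 30% at r = 0.2 and 58% at r = 0.3.

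**Simulation with age alone (1000 runs, 5500 patients, no regimen effect).** Assumed: about 26% mixed, mixed patients about 1.1 years older, mean about 9 oocytes, SD about 6.6, and 3.5% fewer oocytes per year of age. The t-test was significant in 31% of runs and Mann-Whitney in 28%, with a mean spurious difference of −0.30 oocytes. An age-adjusted regression was significant in 5.1%, with a mean difference of 0.01. Adjustment restored the nominal rate here only because the sole confounder was measured and modelled. The simulation also shows that the Mann-Whitney branch, which oocyte counts are likely to take, gives almost no protection.

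**Comparison 2.** It uses only the mono patients, so n is smaller and rejection less frequent for the same imbalance. The spurious gap itself does not shrink with n.

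**The case against.** The strongest reply is that the plan never claims a regimen effect. Its stated goal is to investigate the biosimilar's efficacy in real-world patients. It is openly labelled retrospective and observational, and it states no superiority hypothesis or causal estimand. That is correct. A reader might infer that the sponsor intends to credit a mono-mixed difference to the regimen, but the documents do not say so. What stands is that the plan names two contrasts, tests them at 0.05 under a comparative title, and supplies neither an adjusted analysis nor a statement limiting the interpretation.

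Second, every input except N and alpha is assumed, and the 79% rests on the equal split, which gives the highest rate of the three. This also stands, which is why the less even splits are shown.

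Third, a reader might infer from the word addition in the mixed definition that urinary products were given mid-cycle to women responding weakly, so that the mixed group is bound to look worse. The documents do not say whether these products were planned from the start or added during stimulation, or for what reason. If they were added in response to progress, response itself would help set the group, the bias could run in either direction, and baseline adjustment would remove only part of it. The confounding concern does not depend on this.

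Finally, adjustment cannot cure unmeasured confounding. That is true, and it is a reason to pair it with a statement on interpretation.

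**Conclusion.** The concern holds for comparisons 1 and 2 and for both primary outcomes. As written, a significant difference cannot be separated from differences in who received which regimen. Under the stated assumptions, false rejection for oocytes is 39% to 79% across the three splits at a spurious gap of 0.45. For pregnancy it is 30% to 58% at gaps of 1.9 to 2.8 points with an equal split. These figures show what modest imbalance could do. They do not estimate this study's actual error rate, because the documents report no baseline balance.

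The absence of adjustment is a matter of text and does not rest on these assumptions. The point should be fixed, but it does not undermine the descriptive reporting of the overall cohort.

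**What to change.** 1. Make the main analysis of comparisons 1 and 2 a prespecified regression adjusted at least for age and clinic, plus other baseline prognostic factors where recorded. Use a count model such as negative binomial for oocytes and a logistic model for pregnancy. Keep the unadjusted results as descriptive.
2. Before specifying the pregnancy model, reconcile its definition and denominator. Efficacy evaluation criteria lists endpoints per patient and counts clinical pregnancies up to 6 weeks after transfer, whereas Outcome Measures refers to ongoing pregnancy with embryo transfer as the denominator.
3. State that both comparisons are descriptive associations and that no regimen-effect conclusion will be drawn from a p-value alone, adjusted or not.
4. Where the regimen at the start of stimulation is recorded, add a sensitivity analysis grouped by it. Where it is not, state this as a limitation.

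The cost is SAP text, a little more analysis and a more cautious conclusion; residual unmeasured confounding remains. The fix assumes that patient-level age and clinic are in the anonymized dataset. The documents give only an age range and a clinic count, so this needs confirming first.
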